Age-related degenerative disorders, such as osteoarthritis, are among the diseases with the greatest socio-economic impact; moreover, the increase in life expectancy of the population has led to an increase in the number of people affected by this disease in the last decades [Pelletier et al., 2001]. Osteoarthritis (OA) is a chronic joint degenerative disease characterized by degeneration of hyaline articular cartilage, synovial inflammation and changes in the subchondral bone. There are two forms of OA, primary and secondary; the latter occurs at a later age, tending after 60 years, and is due to the natural process of aging of the joint and / or to events of a traumatic nature. Several other etiopathogenetic factors are involved in the development of this degenerative process including genetic factors, obesity and chronic inflammatory status, and the complex pathogenesis is not yet fully determined. The joints most affected are those of the upper and especially lower limbs and the spine and the symptoms are algia, joint stiffness, muscle tension and instability, which induce the patient to immobility in an attempt to avoid pain; this symptomatology often aggravates the quality of life of elderly patients to produce a depressive state that further complicates the general clinical picture [Pelletier et al 2001; Hunziker, 2001]. The current pharmacological and physiatric treatments are not resolutive of OA and in fact, the prosthetic intervention turns out to be the only solution for the patient. In recent decades, the technology has developed more and more performing joint prostheses, inspired by different mechanical and biological principles, in order to better reproduce joint physiology and improve the efficiency of the implant. Currently the materials used have a long life span, and 90 to 95% of the operated patients have a prosthetic implant survival 10 to 15 years after surgery. However, implants can also fail for several reasons: dislocation, aseptic loosening, peri-prosthetic infections aggravated by sometimes predisposing factors of the patient, such as diabetes, which determine the need to perform a revision surgery [Pelletier et al., 2001]. In spite of this, chondrocyte has a key role in the degradation of hyaline cartilage by: i) an imbalance between its own anabolic and catabolic activity; and ii) to the reduction of the chemical-physical properties, other cellular components are more involved in the subsequent possible failure of the integration of the prosthetic implant. Modifications of the joint microenvironment, the deficiency of the regenerative response of the osteoblasts, the inappropriate activation of the chemochemical network and the activation of the synoviocytes in the inflammatory sense (activation of the pathways of NF-KB, HIF1, BMP, TGF- β , and IGF) they are all conditions and factors that can alter the osseointegrative process of a joint prosthesis [Pelletier et al 2001; Hunziker, 2001; Asahara H. et al., 2016]. The aim of the present study is to identify and evaluate the possible role of miRNAs and long non-coding RNA (lncRNA), modulated in OA, as new biomarkers useful to predict the efficiency of the osseointegration process of the prosthetic implant [Xu et al. 2016; Zhang et al. 2017; Bernard NJ. et al., 2014].

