
Objectives of the study

- Primary Objective

Identification and characterization of miRNAs and LncRNA, from synoviocytes, osteoblasts and chondrocytes isolated from tissue samples obtained from endo or surgery arthro-prosthesis, and related signaling involved in synoviocytes and osteoblasts cross-talk during the osteointegration process through suitable *in vitro* co-culture models [Craig I.J. et al., 2016; Lin Y. et al., 2010].

- Secondary Objectives:

Identification of other biomarkers useful for predicting the efficiency of osseointegration of the implant, through bioinformatics and molecular analysis of miRNAs, LncRNA and proteins secreted or produced by synoviocytes and osteoblasts;

Validation of data obtained on miRNAs and LncRNAs through "gain and loss of" experiments function "in primary cultures and co-cultures.

Study design

The study involves the isolation and cellular, molecular and proteomic characterization of synoviocytes, osteoblasts and chondrocytes from "waste" tissue samples obtained from patients undergoing surgery of endo or arthroplasty for osteoarthritis (Experimental Group) or interventions for other causes such as for example periarticular fracture requiring the implantation of a prosthesis (Control Group) at the Rizzoli-Sicilia Department (Bagheria-Palermo).

Deeper analysis of miRNAs and LncRNAs expressed by the synoviocytes, osteoblasts and chondrocytes will be performed in order to understand their possible involvement in the signaling of HIF1- α , β -catenin, NF-Kb and other pathways of osteogenic differentiation, through suitable experimental *in vitro* models of co-cultures. In particular, we will focus on the cross-talk between synoviocytes and osteoblasts, cell populations involved in the post-surgical articular microenvironment and on which the osteointegration process of the joint prosthesis depends.

Population

Inclusion Criteria:

- 1) Male and Female patients > 40 years old hospitalized for surgery of endo- or arthroplasty for OA (Group OA) or for surgery for joint traumatic diseases (eg femoral neck fractures) requiring the implantation of a prosthesis (Control Group);
- 2) Interval of at least three months from any previous infiltrative treatment of any kind;

3) Patients able to provide written informed consent to the study.

Exclusion Criteria

- 1) Severe cognitive defects or psychiatric disorders;
- 2) Tumor pathologies or concurrent antineoplastic therapies;

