- 3) Autoimmune diseases (rheumatoid arthritis);
- 4) Surgery that involves the joint

Material and Methods

The isolated cells (synoviocytes, osteoblasts and chondrocytes) will be kept in culture under specific conditions in order to allow the isolation of proteins, mRNAs, miRNAs and lncRNAs. Cellular characterizations will be performed using FACS (Partec CyFlow Space), while the molecular characterizations will be obtained with qRT-PCR (Light-Cycler 2.0-Roche). Protein / proteomic analysis will be performed using ELISA (commercial kit), Western blot (ChemiDoc XRS + System, BIORAD) and TRIPLE TOF5600 (AB Sciex). The miRNAs and lncRNAs, identified by molecular biology techniques (qRT-PCR, LINE GENE 9640), the mRNAs and the identified proteins will be analyzed through the use of specific software, such as: TargetScanPrediction, Diana Software, MiRBase and Partec FloMax®. The miRNAs and lncRNAs that will be particularly regulated / modulated following the pathology and the reduced activation of the pathways involved in osteoblastic differentiation, will be investigated, evaluating their involvement in the regulation of HIF1- α , β -catenin, NF-Kb signaling and other possible pathways of osteogenic differentiation. Through in vitro co-culture systems (osteoblasts and synoviocytes isolated from tissues), we will evaluate the role of previously identified miRNAs and lncRNAs, in cross-talk between osteoblasts and synoviocytes isolated from patients with OA. Their role will be validated through "gain and loss of function" experiments in primary cultures and co-cultures.

Statistics

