Multivariate statistical analysis of the results will be performed using R software [R Development Core Team (2008) software. A: A language and environment for statistical computing. R Foundation for Statistical Computing, Vienna, Austria. ISBN 3-900051-07-0, URL <http://www.R-project.org>.] After evaluating the normal distribution homogeneity of the variance of data the appropriate parametric statistical tests will be applied (ANOVA or GLM and Student t test) or in case of non-normality and heteroskedasticity similar non-parametric tests (eg Kruskal-Wallis and Mann-Whitney U test). The proteomics data will be analyzed by principal components analysis using MarkerViewTM 1.2.1 (SCIEX) software. The molecular interaction network between the modulated proteins that are found to be significant will be analyzed with the STRING software v10 (Search Tool for the Retrieval of Interacting Genes / Proteins; <http://string-db.org/>). The sample size was calculated using the G*Power software v.3.1.9.2 (University of Kiel, Germany), considering

a significance level $\alpha = 0.05$ and a power $1-\beta = 0.80$. For the calculation of the effect size we considered the result of variation of *ALPL* gene expression in human mesenchymal stem cells cultured in hypoxic environment (similar to the intra-articular environment) between 3 (FOI: 1.53 ± 0.34) and 7 (FOI: 2.53 ± 0.29) days and presenting an increased expression of miR-675-5p [Costa V. et al, 2017]. The effect size value $d=2.28$ was transformed into $f=1.14$, because the sample size was calculated considering a two-way ANOVA model (patient: healthy / osteoarthritis, experimental culture time: 2 short times). The maximum number of patients to be enrolled is $n=10$ of which $n=5$ osteoarthritic and $n=5$ healthy.

Enrollment Procedures

Patients considered eligible will be enrolled in the study, after providing a written informed consent.

Data Collection

Clinical data will be retrieved by patient's source document

A protocol-specific CRF reporting the results of the analyses will be provided

A CRF is required and should be completed for each included subject.

Ethics

The clinical trial protocol and its documents will be sent before initiating the study to the competent Authorities and Ethics Committees of each participating country for its approval.

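### Controls analysed as healthy are defined only by their reason for surgery; nothing excludes osteoarthritis in their operated joint, so a 5-patient comparator can contain OA tissue

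*Protocol*

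**What the plan says.** All places are in the Protocol.

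- **Statistics.** The sample size rests on a two-way ANOVA with factors "patient: healthy / osteoarthritis, experimental culture time: 2 short times", and at most 10 patients, "of which $n=5$ osteoarthritic and $n=5$ healthy".
- **Population, inclusion criterion 1.** Patients are over 40, with no upper age limit. Controls are those hospitalised "for surgery for joint traumatic diseases (eg femoral neck fractures) requiring the implantation of a prosthesis (Control Group").
- **Study design.** The control definition is wider: "interventions for other causes such as for example periarticular fracture requiring the implantation of a prosthesis (Control Group").
- **Exclusion criteria.** There are four: cognitive or psychiatric disorder, tumour or antineoplastic therapy, autoimmune disease, and "Surgery that involves the joint". None mentions OA.
- **Introduction.** The opening words are "Age-related degenerative disorders, such as osteoarthritis". It then says that the secondary form tends to appear after 60 and attributes it to ageing of the joint, trauma, or both.
- **Material and Methods.** The miRNAs and lncRNAs taken forward are those "regulated / modulated following the pathology and the reduced activation of the pathways involved in osteoblastic differentiation". The later co-culture work concerns "cross-talk between osteoblasts and synoviocytes isolated from patients with OA".

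**The concern.** The analysis label describes the state of the tissue, while the eligibility rule describes why the patient had an operation. The two coincide only if no trauma patient has OA in the injured joint. The Protocol neither requires that nor describes a check for it, and its own account of OA makes coexisting disease foreseeable in an older patient with joint trauma.

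A control with OA pulls the control mean towards the OA mean and, unless all controls are affected alike, adds spread within the control group. Both effects work against detecting a real difference. At stake is the step at which candidate RNAs are chosen partly because they differ with the disease: a true candidate could be missed. With five controls there is little room to absorb one misclassified patient, and an analysis plan cannot undo an enrolment that the Protocol permits.

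**Working it through.** **1. Can a patient with OA in the operated joint enter as a control?** Take a patient over 40 with a femoral neck fracture needing a prosthesis and OA in the same hip.

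- Inclusion 1 is met through the trauma indication. Inclusions 2 (interval since infiltration) and 3 (consent) do not depend on OA.
- Exclusions 1 to 3 do not concern OA.
- Exclusion 4 does not mention OA and cannot separate this patient from any other, since everyone enrolled has joint surgery.
- The Enrollment Procedures section then admits eligible patients on consent, with no later filter.

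The patient is eligible and would be analysed as healthy.

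**2. The plan's own sample size.** Inputs from the Statistics section: alpha 0.05, power 0.80, d = 2.28, f = d/2 = 1.14, 2x2 ANOVA. For a fixed-effects F test with 1 numerator df, noncentrality is N × f² and error df is N − 4.

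- N = 9: power 0.779.
- N = 10: noncentrality 10 × 1.14² = 13.0, critical F(1, 6) = 5.99, power 0.849.

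The stated maximum of 10 reproduces as the smallest N with power of at least 0.80.

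**3. Dilution from one affected control.** This step does not depend on d. If one of five controls carries a fraction w of the OA shift, the control mean moves by w/5 of that shift, so

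contrast retained = 1 − w/5.

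For w = 0.25, 0.50, 0.75 and 1.00 this gives 95%, 90%, 85% and 80%.

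**4. Illustrative power with one affected control.** This borrows d = 2.28. The fraction w is an assumption; the documents give no value.

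| w | contrast (d) | 2x2 F test, mean shift only | t test, 5 v 5, simulated |
|---|---|---|---|
| 0 | 2.28 | 0.85 | 0.88 |
| 0.25 | 2.17 | 0.81 | 0.84 |
| 0.50 | 2.05 | 0.77 | 0.77 |
| 0.75 | 1.94 | 0.72 | 0.67 |
| 1.00 | 1.82 | 0.67 | 0.54 |

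The F-test column uses f = 1.14 × (1 − w/5); at w = 1, f = 0.912 and noncentrality is 8.32. The t-test column (400,000 simulated trials per row, unit SD) falls further because the affected control also adds variance. At w = 1 the expected extra within-group sum of squares is 2.28² × 4/5 = 4.16 on top of 8, so the pooled variance rises from 1 to 12.16/8 = 1.52.

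**5. How likely is at least one affected control?** The documents do not say. With an assumed share q of eligible controls having OA in the operated joint, the chance is 1 − (1 − q)⁵: 41% at q = 10%, 67% at 20% and 83% at 30%.

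**The case against.** The strongest reply is that the power figures show nothing about this study. The number of affected controls and the share of the shift they carry are assumed, and d = 2.28 is a day 3 to day 7 change in *ALPL* expression in stem cells under hypoxia, not a difference between OA and control tissue. The answer also depends on the model: 0.67 or 0.54 for the same patient. This stands. Only the 20% share of the group and the 1 − w/5 dilution are free of d.

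Second, the work is exploratory. The primary objective is to identify and characterise RNAs and their signalling, not to confirm a group difference. A reader might infer that contaminated controls would also undermine the co-culture and gain- and loss-of-function results. The Protocol does not support that: the co-cultures use cells from patients with OA, so a mislabelled control does not affect them directly. What remains is a possible missed candidate at selection.

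Third, *healthy* may be shorthand for non-OA, since the Study design separates the groups by cause of surgery. That is a fair reading of the intent, and renaming alone is mostly wording. But separation by indication is not separation by tissue state, so the gap remains.

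Fourth, a reader might add weight from exclusion 4, which literally fits every enrolled patient. That is a separate drafting defect: it neither causes nor cures misclassification of controls.

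**Conclusion.** The point holds as a gap in the control definition. As written, a patient with OA in the operated joint can be enrolled and analysed as healthy. One such patient is 20% of the comparator and removes up to 20% of the expected OA/control contrast, at a sample size that only just clears its power target on the plan's own terms. The consequence is confined to the exploratory selection of candidates.

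The fall in power from 0.85 to about 0.67 rests on three assumptions: exactly one affected control, that control carrying the full OA shift, and d = 2.28 standing in for an OA/control effect. With mild OA in one control the loss is small. A reader might infer that the controls will be contaminated or that the study is underpowered. The documents give no OA frequency in controls and no OA-versus-control effect, so neither conclusion follows. The change is worth making because it is cheap and must precede enrolment.

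**What to change.** 1. Add an exclusion that applies to controls only: OA of the operated joint documented in the clinical records or reported on existing pre-operative imaging. State the source and the threshold in the Protocol, and apply the criterion before enrolment and before any assay.
2. Record OA status of the operated joint and age for every patient, and report ages by group.
3. Describe the comparator as trauma controls without documented OA, in place of *healthy*, and use the wording of inclusion criterion 1 in the Study design section.

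Separately, exclusion criterion 4 and inclusion criterion 1 must be reconciled.

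**Cost.** One eligibility line, two recorded items and some wording; no new assay and no change to the maximum of 10. Control recruitment may be slightly slower. The Protocol does not say what records or imaging exist for trauma patients, and mild OA may be missed. Because OA is age-related, controls selected to be free of it may be younger than the OA group, so some dilution could be exchanged for confounding by age. The injury itself also remains a difference between groups. Results should be interpreted with age and injury in mind.
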